4. INVESTIGATIONAL PLAN

4.1. Overall Study Design

This is an open-label, nonrandomized, Phase 1/2 study to determine the safety and tolerability, define the MTD or PAD, and assess the preliminary efficacy of INCAGN01876 in subjects with advanced or metastatic solid tumors. Subjects will receive INCAGN01876 on Day 1 of each cycle. Part 1 of the study will begin with 14-day cycles; however, alternate dose administration schedules may also be explored depending on PK, [REDACTED] and safety results. The study will be conducted in 2 parts:

- **Part 1 – Dose Escalation and Safety Expansion** will determine the PAD, defined as a dose that provides a maximal biochemical effect, or [REDACTED], and/or the MTD of INCAGN01876, including defining the optimal dose administration schedule and the maximum number of tolerated doses (MNTD).
- **Part 2 – Dose Expansion** will evaluate the recommended dose and administration schedule determined in Part 1 in subjects with select tumor types [REDACTED] including adenocarcinoma of endometrium, melanoma, NSCLC, and RCC [REDACTED]

See [Figure 2](#) for overall study design.

4.1.1. Part 1 – Dose Escalation

In Part 1, subjects with advanced or metastatic solid tumors who progressed after treatment with available therapies that are known to confer clinical benefit, who are intolerant to treatment, or refuse standard treatment will be enrolled. A 3 + 3 design will be utilized to determine the MTD or PAD of INCAGN01876.

A minimum of 3 evaluable subjects will be enrolled in each cohort beginning with Cohort 1 (0.03 mg/kg; starting dose). There will be a waiting period of 48 hours between dose administration of the first subject and second subject of each dosing cohort. The first 3 evaluable subjects within a cohort will be observed for a DLT observation period of 28 days, before the next cohort begins enrollment. The dose will be escalated if 0 of the first 3 evaluable subjects enrolled has a DLT (see [Section 5.4.2](#)). If 1 of the first 3 evaluable subjects enrolled has a DLT, then the cohort will be expanded to include 3 additional evaluable subjects, and if no DLT occurs in the additional 3 subjects, then the dose will be escalated. If a DLT occurs in one-third or more of the expanded cohort, then the MTD will be deemed to be exceeded, and the previous dose level will be considered the MTD. If only 3 subjects were treated at the MTD or PAD, then a minimum of 3 additional evaluable subjects will be enrolled at this dose before it is administered in Part 2 of the study. If a DLT is experienced in Cohort 8 (20.0 mg/kg) a dose level of 15.0 mg/kg may be explored pending agreement with investigators and sponsor, based on safety data.

If Cohort 1 (0.03 mg/kg; starting dose) exceeds the MTD, the sponsor and investigators will consider dosing INCAGN01876 at 0.01 mg/kg (Cohort -1), and/or investigate 0.03 mg/kg at

alternate dose schedules, based on available safety, PK, [REDACTED] data. If an alternate schedule is tested and determined to be safe, re-escalation of INCAGN01876 will proceed according to [Table 2](#).

Throughout the treatment period, if > 33% of subjects (a minimum of 6 subjects) experience a \geq Grade 3 toxicity related to study drug after completing \geq 4 cycles, then dose administration will be stopped, and the MNTD will be determined in conjunction with the investigators and sponsor based on all available safety data.

Additional subjects will be enrolled in a cohort to achieve the minimum of 3 evaluable subjects. Subjects who drop out for reasons other than a DLT (eg, events clearly associated with the underlying disease, disease progression, concomitant medication, or comorbidity) during the 28-day DLT observation period will be considered nonevaluable and will be replaced. Dose modifications should not be made during the DLT observation period without discussion with the medical monitor. Intrasubject dose escalation is not permitted; however, once the RP2D and schedule has been determined, ongoing subjects in Part 1 may be permitted to escalate to the RP2D with approval of the medical monitor. The cohorts and dose levels are shown in [Table 2](#).

Table 2: INCAGN01876 Dose Levels and Cohorts

Cohort	Dose of INCAGN01876
-1	0.01 mg/kg ^a
1 (starting dose)	0.03 mg/kg
2	0.1 mg/kg
3	0.3 mg/kg
4	1.0 mg/kg
5	3.0 mg/kg
6	5.0 mg/kg
7	10.0 mg/kg
8	20.0 mg/kg

^a Subjects who require a dose reduction below 0.01 mg/kg should be discontinued from study drug.

4.1.2. Part 1 – Safety Expansion

In order to [REDACTED] confirm the preliminary safety of the dose escalation cohorts, Part 1 of the study may include safety expansion cohorts evaluating doses and schedules equivalent to or lower than the highest dose levels determined to be safe and/or doses determined to be pharmacologically active. Fixed doses of INCAGN01876 (equivalent to or less than the MTD/PAD determined during dose escalation), may also be explored during the safety expansion. All doses and schedules explored during the safety expansion will depend on PK, [REDACTED] and safety results.

Approximately 36 evaluable subjects will be enrolled in the Part 1 safety expansion, with each cohort enrolling approximately 9 evaluable subjects. If < 3 of 9 evaluable subjects experience a DLT, then the cohort will be deemed safe. If > 1 safety expansion cohort is deemed safe, then a recommended dose and schedule will be determined in conjunction with the investigators and

sponsor based on all available safety, PK, [REDACTED] results. The safety expansion cohorts may be conducted in parallel to Part 2 and may be limited by the sponsor to subjects with specific tumor types to achieve a balance across cohorts.

[figure not shown]
4.1.3. Part 2 – Dose Expansion

Part 2 of the study will further evaluate the safety, tolerability, preliminary efficacy, PK, and pharmacologic activity of the RP2D of INCAGN01876 in subjects with advanced or metastatic adenocarcinoma of the endometrium, melanoma, NSCLC (squamous and nonsquamous), and RCC. Each cohort will comprise an individual tumor type. A Simon 2-stage design will be utilized with a stopping rule to allow early termination of a particular cohort at the end of Stage 1 if there are insufficient responses observed. During Stage 1, 9 evaluable subjects will be enrolled in each cohort; if no responses are observed within the cohort, then the cohort will be discontinued. If at least 1 response is observed, then 8 additional evaluable subjects will be enrolled in the cohort (Stage 2), for a maximum of 17 evaluable subjects per cohort.

Subjects will continue to receive INCAGN01876 at the RP2D and schedule until Protocol-defined withdrawal criteria are met. Continuous evaluation of toxicity events will be performed throughout enrollment in Part 2 of the study. If the cumulative incidence of DLTs occurs in $\geq 33\%$ of subjects after 6 subjects have been observed for at least 28 days, further enrollment may be interrupted until the sponsor has determined the appropriate course of action. All AEs, regardless of the time of occurrence on study, may be considered in determining the appropriate dose, schedule, and MNTD.

Toxicity will continue to be monitored throughout the treatment period. If $> 33\%$ of subjects (minimum of 6 subjects) experience a \geq Grade 3 toxicity related to study drug after completing ≥ 4 cycles, then the MNTD will be determined in conjunction with the investigators and sponsor based on all available safety data.

Figure 2: Study Design

4.2. Measures Taken to Avoid Bias

This is an open-label study; no formal comparisons will be made between subjects or against historical controls. Measurements of safety and efficacy are objective measurements, and only comparisons to pretreatment conditions will be made.

4.3. Number of Subjects

4.3.1. Planned Number of Subjects

Up to approximately 152 evaluable subjects may be enrolled in the study.

- Part 1 Dose Escalation – Approximately 24 to 48 evaluable subjects
- Part 1 Safety Expansion – Approximately 18 to 36 evaluable subjects
- Part 2 Dose Expansion – Up to 68 evaluable subjects (up to 36 in Stage 1 and up to 32 in Stage 2)

4.3.2. Replacement of Subjects

Subjects may be replaced for any of the following reasons:

- In Part 1, any subject who withdraws from treatment before the completion of the DLT observation period for any reason other than a DLT (is not evaluable for DLTs) (see [Section 5.4.2](#)).
- 
- Subject does not meet the eligibility requirements of the study (eg, accidental enrollment).

See [Sections 9.1](#) and [9.2](#) for additional information regarding replacement of subjects.

4.4. Duration of Treatment and Subject Participation

After signing the ICF, screening assessments may be completed over a period of up to 28 days. Subjects will continue to receive INCAGN01876, up to the defined maximum number of cycles, as long as the subject is deriving benefit and has not met any of the Protocol-defined conditions for treatment withdrawal (see [Section 5.5](#)). If the subject discontinues treatment with INCAGN01876, then the treatment period will end, and the subject will enter the follow-up period (see [Section 6.4](#)). Each subject will be expected to participate in the study for a maximum of 14 months.

4.5. Overall Study Duration

The study begins when the first subject signs the informed consent. The end of the study will occur when all subjects have completed the last study follow-up visit or have discontinued study drug and have completed applicable follow-up assessments.

The end of the study may be declared when no more than 5 subjects remain on study drug for at least 6 months, at which point a database lock of the study may occur to allow for analysis of the study data. Any remaining subjects may continue to receive study drug and be seen by the investigator per standard of care. The investigator will be expected to monitor for and report any serious AEs (SAEs) and pregnancies, as detailed in [Section 8](#). The remaining subjects will be considered on study until a discontinuation criterion is met and written notification is provided to the sponsor.

4.6. Study Termination

The investigator retains the right to terminate study participation at any time, according to the terms specified in the study contract. The investigator is to notify the institutional review board (IRB)/independent ethics committee (IEC) in writing of the study's completion or early termination, send a copy of the notification to the sponsor or sponsor's designee, and retain 1 copy for the site study regulatory file.

The sponsor may terminate the study electively, if required by regulatory decision or upon review of emerging data. If the study is terminated prematurely, then the sponsor or designee will notify the investigators, the IRBs and IECs, and regulatory bodies of the decision and reason for termination of the study.

5. TREATMENT

5.1. Treatment Assignment

5.1.1. Subject Numbering and Treatment Assignment

All subject numbers will be 6 digits; the first 3 digits will be the site number, and the last 3 digits will be the subject's number. This subject number will be maintained throughout the study and will not be reassigned. Subjects who withdraw consent or discontinue from the study after being assigned a subject number will retain their number.

This is a nonrandomized study, in which subjects will be enrolled into either Part 1 or Part 2 as described previously, with all subjects receiving INCAGN01876 (herein referred to as study drug). Site staff will contact the interactive web response system (IWRS) at the time of screening, when enrolling subjects, and when ordering study drug for all treatment cycles, as well as to discontinue subjects from treatment. Refer to the IWRS manual for detailed information.

5.1.2. Randomization and Blinding

This is an open-label nonrandomized study; therefore, randomization and blinding do not apply.

5.2. Study Drug

5.2.1. Description and Administration

The study drug (INCAGN01876) is in liquid form in the formulation buffer of 10 mM histidine, 7% sucrose, pH 6.0 at a strength of 10 mg/mL to be used for IV infusion. The infusion site should not be used for blood sampling.

Study drug will be diluted in 0.9 % normal saline and administered by qualified personnel as an IV infusion over a 30-minute period on Day 1 of each cycle. In Part 1, subjects will be administered study drug, according to cohort enrollment ([Table 2](#)). In Part 2, subjects will be administered study drug at the RP2D and schedule. Subjects will continue to receive INCAGN01876, up to the defined maximum number of cycles, as long as the subject is deriving benefit and has not met any of the Protocol-defined conditions for treatment withdrawal (see [Section 5.5](#)).

Duration of treatment (maximum number of cycles) will be determined based on safety during Part 1 and may be fewer than the absolute maximum number of cycles as outlined below:

- For a 14-day cycle: maximum of 26 cycles
- For a 21-day cycle: maximum of 17 cycles
- For a 28-day cycle: maximum of 13 cycles

The Pharmacy Manual contains additional information and instructions for study drug preparation and infusion.

5.2.2. Supply, Packaging, and Labeling

Study drug will be supplied as 5.0 mL aqueous solution in 10 mL glass vials with 10 mg/mL of INCAGN01876. Study drug will be packaged as open-labelled supplies, each vial will be labelled and placed in a carton. The Pharmacy Manual contains additional information regarding supply, packaging, and labeling of study drug.

The investigator shall take responsibility for and shall take all steps to maintain appropriate records and ensure appropriate supply, storage, handling, distribution, and usage of study drug in accordance with the Protocol and any applicable laws and regulations.

All Incyte investigational product labels will be in the local language and will comply with the legal requirements of each country and will state "Caution: New Drug--Limited by Federal (or United States) law to investigational use."

5.2.3. Storage

Study drug must be stored refrigerated (2-8°C) and protected from light, in a secure, limited-access location. Receipt and dispensing of study drug must be recorded by an authorized person at the study site. Study drug may not be used for any purpose other than that stated in the Protocol. The Pharmacy Manual contains additional information regarding storage of study drug.

5.3. Treatment Compliance

Compliance with study drug dosing will be calculated by the sponsor based on the drug accountability and infusion records documented by the site staff and monitored by the sponsor/designee.

5.4. Treatment Interruptions and Adjustments

5.4.1. Dose Modifications

Selections and modifications to the study drug are planned for dose-escalation cohorts. Dose interruptions and modifications also may occur for individual study subjects. The identification of DLTs will define the doses used in planned cohorts (see [Section 5.4.2](#)). Further, the occurrence of DLTs and other toxicities (related or unrelated to study drug) will guide decisions for treatment interruptions and discontinuation for individual subjects. Intrasubject dose escalation is not permitted; however, once the RP2D has been determined, ongoing subjects in Part 1 may be permitted to dose escalate to the RP2D with medical monitor approval.

5.4.2. Dose-Limiting Toxicity and Determination of a Maximum Tolerated Dose

The evaluation period for DLTs will begin on Cycle 1 Day 1 and will continue up to and including study Day 28. All DLTs will be assessed by the investigator using [CTCAE v4.03](#). A DLT will be defined as the occurrence of any toxicity in [Table 3](#), with the exception of events

clearly associated with the underlying disease, disease progression, a concomitant medication, or comorbidity.

Individual subject dose reductions may be made based on events observed at any time during treatment with study drug; however, for the purposes of dose cohort escalation/de-escalation, expanding a dose cohort, and determining the MTD/PAD of study drug, decisions will be made based on events that are observed from the first day of study drug administration through and including study Day 28. A lower MTD may subsequently be determined based on relevant toxicities that become evident after study Day 28.

Table 3: Definition of Dose-Limiting Toxicity

Nonhematologic toxicity

 • Any \geq Grade 3 nonhematologic toxicity EXCEPT the following: 
 – Transient (\leq 72 hours) abnormal laboratory values without associated clinically significant signs or symptoms. – Nausea, vomiting, and diarrhea adequately controlled with supportive care within 48 hours. – Changes in cholesterol and triglycerides. – An event clearly associated with the underlying disease, disease progression, a concomitant medication, or comorbidity. – Asymptomatic changes in lipid profiles. – Asymptomatic changes in amylase and lipase. – Single or nonfasting elevations in blood glucose (ie, blood glucose excursions will be considered toxicities if fasting blood glucose is elevated on 2 separate occasions).
Hematologic toxicity

 • Grade 3 thrombocytopenia with clinically significant bleeding (ie, requires hospitalization, transfusion of blood products, or other urgent medical intervention). • Grade 4 thrombocytopenia. • \geq Grade 3 febrile neutropenia (absolute neutrophil count $< 1.0 \times 10^9/L$ and fever $> 101^\circ F/38.3^\circ C$). • Grade 4 neutropenia that does not recover to \leq Grade 2 in ≤ 3 days after interrupting study drug. • Grade 4 anemia not explained by underlying disease or some other concomitant disorder.
Immune-related toxicity^a

 • \geq Grade 2 ocular irAEs will be considered a DLT. • Grade 3 irAEs that do not improve to baseline or at least Grade 1 in < 5 days with appropriate care or with corticosteroid therapy will be considered a DLT. • Grade 4 irAEs will be considered a DLT regardless of duration.
General

 • Inability to receive the planned number of doses within the 28-day DLT period due to toxicity, regardless of grade, will be considered a DLT.

Table 3: Definition of Dose-Limiting Toxicity (Continued)

MTD

• In Part 1 of the study, the MTD will be defined as 1 dose level below that at which \geq one-third of subjects in a particular cohort have DLTs.• In Part 2 of the study, toxicities will continue to be monitored. If the cumulative incidence of DLTs occurs in $> 33\%$ of subjects after 6 subjects have been observed for at least 28 days, then further enrollment may be interrupted, and the investigators and sponsor will meet and reassess the MTD. All AEs, regardless of the time of occurrence on study, may be considered in determining the appropriate dose, schedule, and MNTD.
MNTD

• Throughout the treatment period, if $> 33\%$ of subjects (minimum of 6 subjects) experience a \geq Grade 3 toxicity related to study drug after completing ≥ 4 cycles, then dose administration will be stopped, and the MNTD will be determined in conjunction with the investigators and sponsor based on all available safety data.

^a Immune-related AEs are a diagnosis of exclusion, after alternative etiologies have been ruled out.

5.4.3. Management of Dose-Limiting Toxicities or Other Urgent Situations

In all cases, investigators may employ any measures or concomitant medications, after discussion with the sponsor (whenever possible), necessary to optimally treat the subject.

5.4.4. Follow-Up of Dose-Limiting Toxicities

Any DLT should be followed until it resolves to baseline or appears to have stabilized for a minimum of 4 weeks (eg, 28 days). During follow-up, subjects should be seen as often as medically indicated to assure safety.

5.4.5. Procedures for Cohort Review and Dose Escalation

Telephone conferences will be scheduled by the sponsor with study investigators in order to review cohort-specific data and overall safety data, to agree on dose escalation, adjudicate individual high-grade AEs as potentially dose-limiting, and guide other major study decisions.

5.4.6. Criteria and Procedures for Dose Interruptions and Adjustments of Study Drug

Treatment with study drug may be delayed to allow for resolution of toxicity. Subjects may resume treatment if no medical condition or other circumstance exists that, in the opinion of the investigator, would make the subject unsuitable for further participation in the study. For toxicities that occur outside of the 28-day DLT period, the treating investigator should contact the medical monitor to discuss the case of any subject whose treatment has been delayed for more than 4 weeks (28 days) before restarting treatment with study drug.

Instructions for dose modifications and interruptions are outlined in [Table 4](#). Individual decisions regarding dose interruptions and reductions should be made using appropriate clinical judgment in consultation with the medical monitor, taking into account relatedness of the AE to the study drug and the subject's underlying condition. Adverse events that have a clear alternative explanation, or transient (≤ 72 hours) abnormal laboratory values without associated clinically significant signs or symptoms may be exempt from dose-reduction rules. Dose interruptions are permitted in the case of medical/surgical events or logistical reasons not related to study therapy (eg, elective surgery, unrelated medical events, subject vacation, and/or

holidays). Subjects should be placed back on study therapy within 4 weeks (28 days) of the scheduled interruption, unless otherwise discussed with the sponsor. The reason for interruption should be documented in the subject's study record.

Table 4: Rules for Interruption and Restarting of Study Drug

CTCAE Grade or Severity	Timing for Restarting Treatment	Dose Level for Restarting Treatment	Treatment Discontinuation
1-2 (mild-moderate)	Continue treatment at the discretion of the investigator.	N/A	N/A
3 (severe)	Toxicity resolves to Grade 0-1.	Reduce by 1 dose level. ^a	Toxicity does not resolve within 4 weeks (28 days) of last dose, except by approval of the medical monitor. OR Second occurrence of previously resolved Grade 3 AE.
4 (life-threatening)	Permanently discontinue.	N/A	Permanently discontinue.

Note: Permanently discontinue for any severe or Grade 3 AE that recurs or any life-threatening event.

^a No more than 2 dose reductions of study drug are permitted, or 1 dose reduction of study drug if the starting dose is 0.03 mg/kg (see Table 2). Subjects should be permanently discontinued from study drug if they have AEs requiring more than 2 dose reductions of study drug.

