5.4.8. Management of Infusion Reactions

[Table 6](#) shows treatment guidelines for subjects who experience an infusion reaction associated with administration of study drug. Signs and symptoms usually develop during or shortly after drug infusion and generally resolve completely within 24 hours of completion of infusion.

Table 6: INCAGN01876 Infusion Reaction Treatment Guidelines

CTCAE Grade	Treatment	Premedication at Subsequent Dose Administration

Grade 1: Mild reaction; infusion interruption not indicated; intervention not indicated.
	
Increase monitoring of vital signs as medically indicated until the subject is deemed medically stable in the opinion of the investigator.
	
None.

Grade 2: Requires infusion interruption but responds promptly to symptomatic treatment (eg, antihistamines, NSAIDs, narcotics, IV fluids); prophylactic medications indicated for ≤ 24 hours.
	
Stop infusion and monitor symptoms. Additional appropriate medical therapy may include but is not limited to the following:
 
 • IV fluids • Antihistamines • NSAIDs • Acetaminophen • Narcotics 
Increase monitoring of vital signs as medically indicated until the subject is deemed medically stable in the opinion of the investigator.
 
If symptoms resolve within 1 hour of stopping drug infusion, the infusion may be restarted at 50% of the original infusion rate. Otherwise, dose administration will be interrupted until symptoms resolve, and the subject should be premedicated for the next scheduled dose.
 
Subjects who develop Grade 2 toxicity despite adequate premedication should be permanently discontinued from further study drug administration.
	
Subject may be premedicated 1.5 h (± 30 min) prior to infusion with the following:
 
 • Diphenhydramine 50 mg orally (or equivalent dose of antihistamine). • Acetaminophen 500-1000 mg orally (or equivalent dose of antipyretic).

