
Grade 3: Prolonged (ie, not rapidly responsive to symptomatic medication and/or brief interruption of infusion); recurrence of symptoms following initial improvement; hospitalization indicated for other clinical sequelae (eg, renal impairment, pulmonary infiltrates).
	
Stop infusion. Additional appropriate medical therapy may include but is not limited to:
 
 • IV fluids • Antihistamines • NSAIDs • Acetaminophen • Narcotics • Oxygen • Pressors • Corticosteroids • Epinephrine 	
No subsequent dose.

Grade 4: Life-threatening; pressor or ventilatory support indicated.
	
Increase monitoring of vital signs as medically indicated until the subject is deemed medically stable in the opinion of the investigator.
 
Hospitalization may be indicated.
 
Subject is permanently discontinued from further study drug administration.
	

NSAID = nonsteroidal anti-inflammatory drug.

Note: Appropriate resuscitation equipment should be available in the room and a physician readily available during the period of drug administration.

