5.4.9. Criteria for Permanent Discontinuation of Study Drug

The occurrence of an unacceptable toxicity not caused by the underlying malignancy will be presumed to be related to study drug and will require that the study drug be permanently discontinued. Unacceptable toxicity is defined as follows:

- Grade 4 or life-threatening AEs (see [Table 4](#) and [Table 6](#)).
- \geq Grade 2 ocular irAE.
- Occurrence of an AE that is related to treatment with the study drug that, in the judgment of the investigator or the sponsor's medical monitor, compromises the subject's ability to continue study-specific procedures, or is considered to not be in the subject's best interest.
- An AE requiring more than 2 dose reductions of study drug, or more than 1 dose reduction of study drug if the starting dose is 0.03 mg/kg (see [Table 2](#)).
- Persistent AE requiring a delay of study drug beyond 4 weeks (28 days), unless the delay has been approved by the sponsor.

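### Table 4, read alone, lets subjects continue or restart after events for which Section 5.4.9, Table 5 or Table 6 calls for permanent discontinuation, and no order of precedence is stated

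*Protocol*

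**What the plan says.** Section 5.4.6 presents Table 4 as the instructions for modifying and interrupting dose. The table has three rows, defined by CTCAE grade only.

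- Grade 1-2: "Continue treatment at the discretion of the investigator". The discontinuation column reads not applicable.
- Grade 3: dosing may restart when "Toxicity resolves to Grade 0-1", and the dose entry is "Reduce by 1 dose level". Discontinuation follows only if the event has not resolved within 28 days of the last dose (unless the medical monitor approves) or on a "Second occurrence of previously resolved Grade 3 AE".
- Grade 4: permanent discontinuation.

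Other parts of Section 5.4 deal with particular events.

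- Section 5.4.9 lists the toxicities that require permanent discontinuation. One item, with a greater-than-or-equal sign before it, is "Grade 2 ocular irAE". Table 3 in Section 5.4.2 also makes this event dose limiting: "Grade 2 ocular irAEs will be considered a DLT".
- Table 6 in Section 5.4.8 allows no later dose after a Grade 3 infusion reaction, and its treatment text for the severe grades ends with "Subject is permanently discontinued from further study drug administration".
- Table 6 also says, for the Grade 2 row: "Subjects who develop Grade 2 toxicity despite adequate premedication should be permanently discontinued from further study drug administration".
- Table 5 in Section 5.4.7, in its Grade 3-4 row, says that drug should be stopped for good when an irAE is severe or clinically significant.

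**The concern.** A site that opens Table 4 for an ocular irAE, another irAE or an infusion reaction finds a complete-looking instruction and nothing to send it elsewhere. For some of these events that instruction allows further dosing, while another passage calls for a permanent stop.

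These are subject-safety instructions in a trial whose primary endpoint is safety and tolerability (protocol Section 2.2.1). They also feed the reported results. SAP Section 8.2.5 counts subjects with dose reductions and subjects with permanent discontinuation because of TEAEs, and SAP Section 6.4 summarises exposure. A first, resolved Grade 3 infusion reaction could end as a dose reduction under Table 4 or as a discontinuation under Table 6. The same event could then be counted differently at different sites.

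**Working it through.** No arithmetic applies. The check sets the passages side by side.

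| Event | Table 4, read alone | Other passage |
|---|---|---|
| Ocular irAE, Grade 2 | May continue; discontinuation not applicable | Section 5.4.9: permanent discontinuation required |
| Ocular irAE, Grade 3, first and resolved | May restart one level lower | Section 5.4.9: permanent discontinuation required |
| Infusion reaction, Grade 3, first and resolved | May restart one level lower | Table 6: no later dose |
| Infusion reaction, Grade 2 despite premedication | May continue; discontinuation not applicable | Table 6: permanent discontinuation |
| Other irAE, Grade 3, first and resolved | May restart one level lower | Table 5: permanent discontinuation if severe or clinically significant |
| Any event, Grade 4 | Permanent discontinuation | Section 5.4.9 and Table 6 agree |

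The five mismatched lines form four classes of event, because the ocular rule reaches two rows of Table 4. On the irAE line, Table 4 itself labels Grade 3 as severe.

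**Does Table 4 send the reader elsewhere?** Its note repeats the rule for recurrent Grade 3 and life-threatening events. Its footnote limits the number of dose reductions and refers to Table 2. Neither mentions Table 5, Table 6 or Section 5.4.9. The text of Section 5.4.6 may exempt AEs with a clear alternative cause and brief laboratory abnormalities from dose reduction, but that does not address the events above.

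**Does Section 5.4.9 close the gap?** It refers to Tables 4 and 6 only in its item on Grade 4 or life-threatening AEs. It does not name the two infusion-reaction cases. An item that rests on the judgment of the investigator or medical monitor could take them in.

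**Is precedence stated anywhere?** No. The nearest text is Section 5.5.1, which makes withdrawal from drug mandatory for unacceptable toxicity. It cites Section 5.4 as a whole, which includes Table 4, and does not rank its parts.

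**Does the layout of Table 6 matter?** The sentence on permanent discontinuation follows the Grade 4 entry when the table is read as plain text, and probably belongs to a cell shared by Grades 3 and 4. The Grade 3 row has its own entry ruling out a later dose, so the mismatch does not depend on this.

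**The case against.** The best defence is that this is a missing cross-reference and no more. Table 4 is worded as permission: the Grade 1-2 row leaves continuation to the investigator, and the text of Section 5.4.6 says that subjects may resume if nothing makes them unsuitable. Sections 5.4.9 and 5.5.1 are mandatory, and Table 6 is specific to one kind of event. The ordinary reading is that a mandatory or specific rule limits a general discretion. Decisions on interruption and reduction are also to be taken with the medical monitor, and suspected irAEs should be discussed with the monitor when possible.

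Much of this stands. A site that stops drug in any of the four classes complies with every passage. A site that continues after a Grade 2 ocular irAE breaches Sections 5.4.9 and 5.5.1. Consultation with the medical monitor would catch many cases. A reader might infer that the protocol as a whole lets a subject with a dose-limiting ocular event keep receiving drug. It does not; only Table 4 taken alone does.

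A reader might also infer that Section 5.4.9, by leaving out the infusion-reaction cases, joins Table 4 in permitting what Table 6 forbids. The documents do not support that either. Section 5.4.9 lists reasons to stop, and absence from that list grants no permission.

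The defence fails where it relies on an unwritten convention. For Grade 3 or 4 hypothyroidism, Appendix B allows hormone replacement without interrupting treatment, whereas Table 4 and Section 5.4.9 stop drug permanently at Grade 4. There, a convention that the specific text governs and a convention that the mandatory text governs give opposite answers. A reader cannot safely supply either one.

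**Conclusion.** The point holds as a matter of internal consistency, and the text is wrong as written. Table 4, read alone, permits further dosing in four classes of event for which Section 5.4.9, Table 5 or Table 6 calls for permanent discontinuation. Nothing states which governs. It should be corrected because the events bear on subject safety.

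Its practical size is unknown. The documents give no frequency for these events, so no effect on discontinuation counts or exposure can be calculated. The conclusion rests on two readings: that Table 4 applies to every adverse event, as Section 5.4.6 presents it, and, for Table 5 only, that severe corresponds to Grade 3, as Table 4 labels it. Table 5 is the weakest of the four, since Section 5.4.7 introduces it as suggested supportive care. It may nevertheless reach the most events, because it is not limited to one organ or to infusion reactions.

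It would go too far to say that the passages give opposite commands. The conflict is between a permission and a stop.

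**What to change.** The sponsor should reconcile Table 4, Table 5, Table 6 and Section 5.4.9 so that each event has one instruction. Table 4 should then carry a statement of precedence and cross-references to the other three passages. Whether the Section 5.4.9 list needs to name the infusion-reaction cases follows from that decision. The Appendix B text on Grade 4 hypothyroidism should be checked in the same pass.

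Which clinical rule applies to each event is for the sponsor and investigators to decide, and the wording should not presume the answer. The cost is a few lines at the next protocol amendment, with no change to the sample size or to the planned analyses.
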